6.3.16. Pneumonia

All suspected pneumonias will require confirmation as defined by the presence of new infiltrate(s) on chest x-ray AND at least 2 of the following signs and symptoms:

- Increased cough
- Increased sputum purulence (color) or production
- Auscultatory findings of adventitious sounds (e.g. egophony, bronchial breath sounds, rales, etc.)
- Dyspnea or tachypnea
- Fever (oral temperature > 37.5 °C)
- Elevated WBC (>10,000/mm³ or >15% immature forms)
- Hypoxemia (HbO₂ saturation ≤88% or at least 2% lower than baseline value)

All pneumonias must be captured on the AE/SAE page of the eCRF and on the pneumonia page of the eCRF.

The investigators and site staff should remain vigilant for the possible development of pneumonia in patients with COPD as the clinical features of such infections overlap with the symptoms of COPD exacerbations. Risk factors for pneumonia in patients with COPD receiving fluticasone furoate/vilanterol include current smokers, patients with a history of prior pneumonia, patients with a body mass index < 25 kg/m² and patients with an FEV₁ < 50% predicted. For all suspected cases of pneumonia, Investigators are strongly encouraged to confirm the diagnosis (this includes obtaining a chest x-ray) and to initiate appropriate therapy as promptly as possible. All diagnoses of pneumonia (radiographically confirmed or unconfirmed) must be reported as an AE or SAE (if applicable).

Note: Pulse oximetry should be measured at any time a moderate or severe exacerbation is reported or pneumonia is suspected and recorded in the source documents and on the pneumonia page of the eCRF if applicable.

6.3.17. Radiography (Chest X-Rays)

Confirmation by chest x-ray (posteroanterior and lateral) should be performed as soon as possible and preferably within 48 hours of suspected pneumonia and/or moderate or severe exacerbation. All chest x-rays will be over-read by a central vendor to confirm the presence of new radiographic findings compatible with pneumonia. In all cases, the signs and symptoms that were used to identify the pneumonia must be documented in the source documents and eCRF. Diagnoses of pneumonia must be recorded as adverse events in the eCRF.

6.3.18. Oropharyngeal Examinations

Oropharyngeal examinations for clinical evidence of infection (*e.g.* *Candida albicans*) will be performed at each study visit as shown in the Time and Events Table. If there is evidence of infection, appropriate therapy should be instituted at the discretion of the Investigator. Subjects may continue in the study on appropriate anti-infective treatment at the discretion of the Investigator. The results of these assessments, and any resulting pharmacotherapy, will be recorded in the subject's clinic notes and in the eCRF. All suspected cases of candidiasis must be reported as adverse events.

6.3.19. Pulse oximetry

Pulse oximetry will be conducted at randomization and recorded in the eCRF. Pulse oximetry should be measured at any time a moderate or severe exacerbation is reported or pneumonia is suspected and recorded in the source documents and on the pneumonia page of the eCRF if applicable.

6.4. Health Outcomes

All patient reported outcomes should be administered at the beginning of a study visit before any physical activity or spirometry. SGRQ-C should be administered first followed by BDI/TDI, EQ-5D-5L, CAT, Subject Global Rating of Activity Limitation and Subject Global Impression of Change in Activity Limitation and Subject Global Rating of COPD Severity and Subject Global Rating of Change in COPD. (See Section 6.2.6 for information on SGRQ-C, Section 6.2.9 for BDI/TDI, Section 6.2.10 for CAT, Section 6.2.11 for Activity limitation and change in activity limitation and Section 6.2.12 for COPD severity and change in COPD).

6.4.1. EuroQol Questionnaire (EQ-5D-5L)

The EQ-5D-5L questionnaire will be completed by subjects at randomization, at Week 28 and Week 52 (or IP Discontinuation Visit).

The EQ-5D-5L is a standardised instrument for use as a measure of health utility. It is designed for self-completion and is cognitively simple, taking only a few minutes to complete. The EQ-5D-5L is a two-part self-assessment questionnaire. The first part consists of five items covering five dimensions (mobility, self care, usual activities, pain/discomfort, and anxiety/depression). Each dimension is measured by a five-point Likert scale (no problems, slight problems, moderate problems, severe problems, and extreme problems). Respondents are asked to choose one level that reflects their "own health state today" for each of the five dimensions. Respondents can be then classified into one of 243 distinct health states. The second part is a 20-cm visual analogue scale (EQ-VAS) that has endpoints labelled "best imaginable health state" and "worst imaginable health state" anchored at 100 and 0, respectively. Respondents are asked to indicate how they rate their own health by drawing a line from an anchor box to that point on the EQ-VAS which best represents their own health on that day. EQ-5D-5L health states are converted to a single summary index by applying a formula that essentially attaches weights to each of the levels in each dimension. The formula is based on the valuation of EQ-5D health states from general population samples.

6.4.2. Healthcare resource utilisation

All unscheduled visits to a physician office, visits to urgent care, visits to emergency department, and hospitalizations will be recorded in the eCRF. In addition visits and contacts that are due to a COPD exacerbation will be assessed and recorded. Patients will be provided with a paper worksheet diary to record any health care contacts between clinic visits. In addition, the paper worksheet diary will be used by subjects to record any medications they have taken or adverse events they have experienced.

6.5. Pharmacokinetics

Concentrations of FF, UMEC and VI in plasma will be determined using currently approved assay methodology under the control of GSK PTS-DMPK. A population pharmacokinetics approach will be employed in this study with samples collected in approximately 300 subjects (to achieve approximately 120 subjects treated with FF/UMEC/VI). At Visits 4 and 5, two 6mL blood samples will be collected from each of the 300 subject as follows:

Visit 4: Predose and in the window 5 to 15 minutes post-dose

Visit 5: In the windows 5 to 15 minutes and 45 to 90 minutes post-dose

Refer to the SPM for details of the sample collection, information to document and treatment, shipment and processing procedures. Raw data will be archived at the bioanalytical site (detailed in the SPM).

6.6. Genetic Research

Information regarding genetic research is included in [Appendix 1](#).

Note: No study centers in China will participate in genetic research in this study.

6.7. Novel Biomarkers

Plasma samples will be collected at Week 16 to analyze fibrinogen, a known inflammatory marker.

After completion of the clinical trial, an exploratory analysis will be conducted on the relationship of plasma fibrinogen with measures of response to each study treatment. The results gained may also be of application for future COPD trials.

7. DATA MANAGEMENT

For this study subject data will be entered into GSK defined electronic case report forms (eCRFs), transmitted electronically to GSK and combined with data provided from other sources in a validated data system.

Management of clinical data will be performed in accordance with applicable GSK standards and data cleaning procedures to ensure the integrity of the data, e.g., removing errors and inconsistencies in the data. Adverse events and concomitant medications terms will be coded using Medical Dictionary for Regulatory Activities (MedDRA) and an internal validated medication dictionary. eCRFs (including queries and audit trails) will be retained by GSK, and copies will be sent to the Investigator to maintain as "the investigator copy". In all cases, subject initials will not be collected or transmitted to GSK according to GSK policy.

8. DATA ANALYSIS AND STATISTICAL CONSIDERATIONS

8.1. Hypotheses

The primary objective of this study is to evaluate the efficacy of FF/UMEC/VI to reduce the annual rate of moderate and severe exacerbations compared with dual therapy of FF/VI or UMEC/VI in subjects with COPD over a 52 week period.

The aim of this study is to demonstrate the contribution of the ICS when used in combination with a fixed dose of a LABA/LAMA, and the contribution of the LAMA above the efficacy of an ICS/LABA combination, in reducing the rate of on-treatment moderate and severe exacerbations in patients with COPD. This is a superiority study.

The primary endpoint is the annual rate of on-treatment moderate and severe exacerbations (calculated as the number of moderate and severe exacerbations during the treatment period).

The primary analyses will be the pair-wise comparisons of FF/UMEC/VI against FF/VI and against UMEC/VI, with inferences adjusted for multiplicity as described in Section 8.3.3. The primary analyses will be based on a two-sided hypothesis testing approach. The hypotheses associated with the statistical test of the primary efficacy endpoint are $H_0: \lambda_T/\lambda_D=1$ versus $H_A: \lambda_T/\lambda_D \neq 1$ where λ_T is the annual rate for triple therapy (FF/UMEC/VI) and λ_D is the annual rate for the respective dual therapies (FF/VI and UMEC/VI).

8.2. Study Design Considerations

8.2.1. Sample Size Assumptions

Sample size calculations are based on the co-primary endpoints, the annual rate of on-treatment moderate and severe exacerbations for the comparison of FF/UMEC/VI with FF/VI and with UMEC/VI.

The treatment benefit for moderate and severe exacerbation rates when adding the ICS component to a LABA in studies with Advair™/Seretide™ [Ferguson, 2008] and with FF/VI [Dransfield, 2013] were approximately 20-30%, where all subjects were restricted from concomitant LAMA therapy. It will be assumed that the ICS effect will be largely maintained even on a background of dual bronchodilation (LABA/LAMA), therefore the study will target a treatment benefit of 15% for FF/UMEC/VI versus UMEC/VI.

As an estimate of dual bronchodilator effect, the SPARK study [Wedzicha, 2013] showed a benefit of a dual bronchodilator over LAMA monotherapy to be approximately 10-12%.

The annual rate of on-treatment moderate and severe exacerbations in the FF/VI treatment arm was 0.92 based on those subjects in the FF/VI arms from the FF/VI Phase IIIa program who can be classified as 'high risk' (unpublished data: studies HZC102871 and HZC102970) according to the most recent COPD guidelines [GOLD, 2013]. Based on these data, the exacerbation rate for FF/UMEC/VI in the current study is estimated to be 0.80 for purposes of sample size calculations, with the estimate for FF/VI being 12% higher (approximately 0.91) and the estimate for UMEC/VI being 15% higher (approximately 0.94). The co-primary endpoints will be controlled for multiplicity using the truncated Hochberg method [Dmitrienko, 2008]. In order to have 90% power to detect a 15% reduction in the annual rate of moderate and severe exacerbations in the FF/UMEC/VI arm compared with the UMEC/VI arm and a 12% reduction compared with the FF/VI arm, 4000 subjects will be randomized to each of the FF/UMEC/VI and FF/VI arms, along with 2000 subjects to the UMEC/VI arm. Calculations are based on a negative binomial regression and use a two-sided 1% significance level in order to satisfy regulatory requirements of substantial evidence of efficacy for a single study. For the multiplicity hierarchy, a 2-sided 5% risk associated with incorrectly rejecting the null hypothesis (significance level) is considered acceptable for this study. The estimate of the dispersion parameter for the negative binomial model is 0.75, which is similar to that seen with fluticasone propionate/salmeterol in the TORCH study [Calverley, 2007] and the dispersion in the FF/VI exacerbation program [Dransfield, 2013].

Subjects will be randomized in a 2:2:1 proportion to the FF/UMEC/VI, FF/VI and UMEC/VI arms, respectively. All randomized subjects (approximately 10,000 in total) are considered to be evaluable for the measurement of exacerbations, irrespective of whether they permanently discontinue from IP. Assuming a 38% screen failure rate, based on the FF/VI Phase III exacerbation program, it is estimated that approximately 16,000 subjects will be screened.

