8.2.2. Sample Size Sensitivity

If the annual rate of moderate and severe exacerbations in the FF/UMEC/VI treatment arm is different from the 0.8 used in the sample size calculation, the power to detect the change in exacerbations rates will be affected.

Table 5 illustrates the power which would be obtained from various moderate and severe exacerbation rates and rate reductions for the FF/UMEC/VI treatment arm compared with the FF/VI treatment arm. The sample size, dispersion factor and two-sided significance threshold of 1% remain fixed.

Table 5 Power for varying FF/UMEC/VI exacerbation rates and treatment improvements versus FF/VI

FF/UMEC/VI rate	True Rate of Exacerbation Improvement, FF/UMEC/VI versus FF/VI		
	8% Reduction	10% reduction	12% reduction
0.90	51%	76%	92%
0.80	47%	72%	90%
0.70	43%	67%	87%
0.60	38%	62%	82%

Table 6 illustrates the power which would be obtained from various moderate and severe exacerbation rates and rate reductions for the FF/UMEC/VI treatment arm compared with the UMEC/VI treatment arm. The sample size, randomization ratio (2:1), dispersion factor and two-sided significance threshold of 1% remain fixed.

Table 6 Power for varying FF/UMEC/VI exacerbation rates and treatment improvements versus UMEC/VI

FF/UMEC/VI rate	True Rate of Exacerbation Improvement, FF/UMEC/VI versus UMEC/VI		
	10% reduction	12% reduction	15% reduction
0.90	53%	75%	94%
0.80	49%	71%	92%
0.70	45%	66%	89%
0.60	40%	60%	85%

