8.2.3. Sample Size Re-estimation

Blinded evaluation of exacerbation rates is planned for this study. A blinded evaluation of exacerbation rates for the purpose of sample size re-estimation will be done after one year of enrolment, or when 5,000 subjects have been randomized, whichever is earlier. A subsequent evaluation will be done after approximately 18 months of enrolment, or when 7,500 subjects have been randomized, whichever is earlier.

If the exacerbation rates for the study are lower than planned, a sample size re-estimation may be conducted. Any subsequent change to the planned number of subjects randomized would be documented in a protocol amendment.

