8.3.5. Key Elements of Analysis Plan

8.3.5.1. Efficacy Analyses

The primary efficacy endpoint of the annual rate of on-treatment moderate and severe exacerbations will be analyzed using a generalized linear model assuming the negative binomial distribution, with the logarithm of time on treatment as an offset variable. The model will include terms for treatment group, gender, exacerbation history (one, two or more), smoking status at screening, baseline disease severity (as % predicted FEV₁) and geographical region. The adjusted mean annual rates, pair-wise treatment ratios and associated p-values and confidence limits will be presented. The fit of the negative binomial model will be examined using “Q-Q” plots of standardized residuals with simulated envelopes.

For the co-primary endpoints, sensitivity analyses will be performed where all available data collected until the time of study withdrawal will be used. For these sensitivity analyses, the total number of events and the total time in the study (both on-treatment and post-treatment) prior to study withdrawal will be used in the analysis model. Imputations made for the period following study withdrawal will be described in the RAP. Additional sensitivity analyses using multiple imputation methods will be described in the RAP.

The secondary endpoints of trough (pre-dose AM) FEV₁ and SGRQ total score will be analysed using mixed models repeated measures with covariates of treatment group, smoking status at screening, baseline, region, and visit, plus interaction terms for visit by baseline and visit by treatment group.

The secondary endpoints involving time to first moderate and/or severe exacerbation will compare the treatment groups using Cox's proportional hazards model, adjusting for treatment group, gender, exacerbation history (one, two or more), smoking status at screening, baseline disease severity (as % predicted FEV₁), and geographical region.

Secondary and other endpoints involving the annual rate of exacerbations will be analysed as described for the primary endpoint.

The additional endpoint of time to onset of multiple moderate and severe exacerbations will be analysed using an Anderson-Gill model for time to recurrent events.

Full details of the analyses to be performed on all primary, secondary and other efficacy endpoints will be given in the RAP.

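### Do the 90% power claim and Tables 5 and 6 of the protocol conflict with the sample size inputs that the protocol states?

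*Protocol*

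**What the plan says.** Protocol Section 8.2.1 gives the ingredients of the calculation. "Calculations are based on a negative binomial regression and use a two-sided 1% significance level". The triple-therapy rate is 0.80 per year, the dispersion is 0.75, and the arms hold 4,000, 4,000 and 2,000 subjects. The size is chosen "In order to have 90% power to detect a 15% reduction in the annual rate of moderate and severe exacerbations" against UMEC/VI and "a 12% reduction compared with the FF/VI arm". The FF/VI rate is introduced "with the estimate for FF/VI being 12% higher (approximately 0.91"; UMEC/VI is described in the same way as 15% higher, at about 0.94. All randomised subjects "are considered to be evaluable for the measurement of exacerbations, irrespective of whether they permanently discontinue from IP".

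Section 8.2.2 varies the rate and the reduction in Tables 5 and 6. For Table 5 it says: "The sample size, dispersion factor and two-sided significance threshold of 1% remain fixed"; for Table 6 it also fixes the 2:1 ratio. The base cases are 90% (Table 5, rate 0.80, 12% reduction) and 92% (Table 6, rate 0.80, 15% reduction).

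Section 8.3.5.1 fits the primary model "with the logarithm of time on treatment as an offset variable". Section 8.2.3 adds a blinded look at exacerbation rates: "If the exacerbation rates for the study are lower than planned, a sample size re-estimation may be conducted".

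**The concern.** A negative binomial power calculation needs a follow-up time per subject, and Section 8.2 gives none. A reader who fills the gap with the planned 52 weeks cannot reproduce any of the 24 printed cells: every one is too low, and the base cases miss by about 4 points. The sentence about evaluability can be read as promising full follow-up, which would make the tables look wrong. The percentages attached to the comparator rates do not match those rates either.

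At stake would be the basis of the sample size and of the blinded re-estimation. On full-year exposure, 90% power against FF/VI needs about 3,506 subjects per arm, not 4,000, and it holds down to a triple-therapy rate of about 0.65. Table 5 already shows 87% at 0.70. Someone re-estimating from the written inputs alone could reach a different answer from someone using the tables.

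**Working it through.** **Inputs.** From Protocol 8.2.1: rate on triple λT = 0.80; reductions 12% and 15%; dispersion k = 0.75; n = 4,000, 4,000 and 2,000; two-sided 1%, so z = 2.576. Mean exposure t is not given and has to be assumed.

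**Comparator rates.** 0.80/0.88 = 0.909 and 0.80/0.85 = 0.941, which are the printed 0.91 and 0.94. By contrast 0.80 × 1.12 = 0.896 and 0.80 × 1.15 = 0.92. The printed rates therefore follow from the stated reductions. They are 13.6% and 17.6% above 0.80 (1/0.88 = 1.136; 1/0.85 = 1.176), and only the percentage labels are off.

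**Formula.** Wald test on the log rate ratio:

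V = (1/(λT·t) + k)/nT + (1/(λD·t) + k)/nD; power = Φ(|ln RR|/√V − 2.576).

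|ln 0.88| = 0.1278 and |ln 0.85| = 0.1625.

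**Reproducing the printed figures, t = 0.8 year (assumed).**
- FF/VI: V = (1.5625 + 0.75)/4000 + (1.375 + 0.75)/4000 = 0.001109; √V = 0.0333; 0.1278/0.0333 = 3.838; power = Φ(1.262) = 89.7% (printed 90%).
- UMEC/VI: V = (1.5625 + 0.75)/4000 + (1.328 + 0.75)/2000 = 0.001617; √V = 0.0402; ratio 4.041; power = Φ(1.465) = 92.9% (printed 92%).

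**Full year, t = 1 (assumed).**
- FF/VI: V = (1.25 + 0.75)/4000 + (1.10 + 0.75)/4000 = 0.0009625; √V = 0.0310; ratio 4.120; power = Φ(1.545) = 93.9%.
- UMEC/VI: V = (1.25 + 0.75)/4000 + (1.0625 + 0.75)/2000 = 0.001406; √V = 0.0375; ratio 4.334; power = Φ(1.758) = 96.1%.

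**All 24 cells, calculated minus printed, in percentage points.**

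| Assumption | Table 5 | Table 6 |
|---|---|---|
| t = 1 | +3.5 to +7.9 | +3.2 to +9.6 |
| t = 0.8 | −1.1 to +0.1 | +0.7 to +1.5 |
| t = 0.806, pooled null variance | −0.7 to +0.3 | −0.1 to +0.7 |
| t = 1, 13% fewer subjects, pooled null variance | −0.8 to +0.5 | −0.3 to +0.8 |

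The last two rows fit equally well (root-mean-square error about 0.4 points each). A linear effect measure (1 − RR) with the null variance taken at the triple-therapy rate also brings every cell within 1.3 points, with t, k and n all left as stated. The tables alone cannot tell these apart.

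**Sample size against FF/VI for 90% power.** n per arm = (2.576 + 1.282)² × S / 0.1278², where S is the sum of the two bracketed terms. For t = 1, S = 3.85 and n ≈ 3,506. For t = 0.8, S = 4.4375 and n ≈ 4,040, close to the planned 4,000.

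**The 90% sentence taken alone.** Read as the power to win both comparisons at 1% with a full year each, allowing for the shared triple arm, it comes to 90.9%. That does not explain the pairwise tables, but the sentence by itself is not shown to be wrong.

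**The case for a change.** The best case for a change runs as follows. Exposure is a required input, the section omits it, and Section 8.2.2 says the sample size and dispersion are held fixed, which leaves exposure as the most natural missing term. If exposure drives the power, a blinded review confined to rates overlooks one of its determinants. The protocol should then state the value, correct the percentages, and add pooled exposure and dispersion to the review.

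Part of this stands. Some allowance, or a different formula, lies behind the tables and is not written down, and the percentage labels are wrong. Shorter exposure is the most plausible candidate.

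It does not carry further. The evaluability sentence says which subjects count, not how long each is observed. Section 8.2.1 sizes the trial on the on-treatment rate, Section 8.3.5.1 uses time on treatment as offset, SAP Section 11.5.1.5.2 ends the at-risk period the day after treatment stops, and the SAP synopsis speaks of up to 52 weeks of treatment. A mean exposure below one year agrees with all of these, so there is no contradiction to resolve.

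The re-estimation in Section 8.2.3 has no numeric trigger, is discretionary, and would change the size only by amendment. The sponsor would presumably work from the calculation behind its own tables. SAP Section 2.3 describes the look as a blinded review of exacerbation data; adding exposure and dispersion to it would be a reasonable extra, not the repair of a fault.

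The literal reading of 12% and 15% higher, which would give 85.8% and 87.2% power, is ruled out by the printed rates and the stated reductions.

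**Conclusion.** No change is called for. The gap of 3.2 to 9.6 points per cell, about 4 points at the two base cases, arises only when a full year of exposure is supplied by the reader. The documents do not state that assumption, and the on-treatment endpoint makes a shorter mean exposure likely. With 0.8 year the printed power and the 4,000 per arm both come out closely, though the documents do not establish that this was the value used.

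The direction is conservative: the printed power is below what full exposure would give, so underpowering is not shown. Error control, the primary model and enrolment are untouched. The percentage labels are a clerical slip beside correct rates. Recording the exposure assumption and the formula would help a reader, but would alter no result, sample size or conclusion.

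This rests on the standard Wald calculation for the log rate ratio and on taking the printed rates, dispersion and arm sizes as the intended inputs.
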